9.2. Analysis Sets

Population	Description
Intent-to-treat (ITT)	
 • All randomized participants will be included in the analyses according to the intervention arm they were assigned,

Population	Description
	regardless of treatment initiation, discontinuation or switching.
On treatment population and on-treatment period	
 All randomized participants who took the assigned treatment will be included in the analyses according to the intervention arm they were assigned until they switch or discontinue the assigned treatment regimen. Follow-up will be censored 5 days after treatment switching or discontinuation, i.e. all events occurring until 5 days after discontinuation or switching to the other treatment group will be attributed to the randomized group and all events occurring later than 5 days after discontinuation or switching will be censored. Participants in the usual care arm who start dronedarone drug therapy will be considered to have switched treatment regimen. Participants in the dronedarone arm who temporarily suspend or are non-adherent with dronedarone for >14 consecutive days will be considered to have discontinued treatment.

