The study intervention will be treatment with oral dronedarone 400 mg twice daily in addition to usual care. The comparator arm will be usual care alone. Usual care will be defined as best-practice, guideline-directed therapy of AF, including but not limited to (a) stroke prevention therapy, (b) rate-control, and (c) treatment of risk factors. More specifically, oral anticoagulation in those men with a CHA₂DS₋₂VASc score of 2 or greater or women with a CHA₂DS₋₂VASc score of 3 or greater, rate control, and treatment of concomitant cardiovascular conditions (e.g. coronary artery disease or heart failure) will be required in all trial participants. As defined in the protocol, those randomized to the dronedarone arm will be prescribed 400 mg oral dronedarone twice daily. Similar to the approach in the EAST trial, those randomized to usual care alone will initially be treated without rhythm-control therapy¹⁴, however rhythm-control therapy (except dronedarone) may be initiated during follow-up in the usual care arm to ameliorate AF-related symptoms despite adequate rate-control therapy per current guideline recommendations. In the dronedarone arm concomitant digoxin use is contraindicated due to P-gp interaction based upon data from the PALLAS trial.²⁹

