6.2. Study Intervention Compliance

The intervention will be prescribed by the treating physician. Study drug will be supplied as part of the study. Participants in the intervention arm will have the study drug prescription generated on their behalf by the PI or treating physician. The study team will communicate with the Central Pharmacy vendor to initiate the study drug kit request and shipment direct to the subject's mailing address of choice. Subjects in the intervention arm will be contacted within 10 days of randomization to verify that they have received their study drug shipment and have started taking their prescription for dronedarone. Participants will self-administer the study intervention at home. Subjects in the intervention arm will receive 3 study drug kit shipments throughout their participation in the trial. Each study drug kit shipment will contain 4-months of study drug supply. Study drug compliance will be assessed at each visit. There is one guideline-recommended therapeutic dose of dronedarone. Any deviation(s) from the prescribed dosage regimen should be recorded. At the end of the study, the patient's physicians will determine whether to stop or continue dronedarone.

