9.3.2. Primary Efficacy Estimand Analysis

Question of Interest	Does the treatment with dronedarone on top of usual care reduce cardiovascular hospitalization or death from any cause in patients with first-detected atrial fibrillation without heart failure compared to usual care alone?
Objective Description / Study Population	Primary objective of the study / All randomized participants
Endpoint	Time from randomization to the first occurrence of unplanned cardiovascular hospitalization or death from any cause within 12 months of randomization

Intercurrent Events	Early study withdrawal or lost-to-follow-up: follow-up will be censored at the last date when patient event status was known. Analysis will assume that censoring is non-informative. All other intercurrent events will be ignored in these analyses.
Population Summary	Hazard ratio estimate based on a Cox proportional hazards model. Values below 1.0 suggest benefit from the treatment with dronedarone and usual care versus usual care alone.

The Cox proportional hazards model will be fit for time to first event with the treatment group as exposure variable. The treatment effect will be presented as a hazard ratio (dronedarone on top of usual care vs. usual care) and a 95% CI and P-value.

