9.3.7. Other Analyses

On treatment analysis of efficacy endpoints

As sensitivity analyses, the primary and key secondary objectives will be tested using the OT population during the on-treatment period.

Pre-Specified Subgroups of Interest

Subgroup analyses for the primary outcome will be performed to assess whether the therapeutic effect is consistent across all patients, or whether it varies according to specific patient

characteristics. These analyses will focus on whether the relative therapeutic effect differs according to the following baseline variables:

- Age (<70 years vs. ≥70 years)
- Sex (male vs. female)
- Race (white vs. racial minorities)
- AF type (paroxysmal vs. persistent, or long-standing persistent)
- Left atrial dimension (<50 mm versus ≥50 mm)
- AF duration (<30 days versus ≥30 days)
- Structural heart disease (present vs. absent)
- Hypertension (present vs. absent)
- Chronic kidney disease (estimated eGFR ≤60 vs. >60 ml/min)
- CHA₂DS₂-VASc score (0-1 vs. ≥2 excluding sex)
- Sleep Apnea (present vs. absent)
- BMI (<30 vs. ≥30)
- Heart failure vs no heart failure
- Left ventricular ejection fraction (LVEF) (41-55 vs. >55)
- Recent hospitalization for AF vs None

Cox proportional hazards regression modeling will be used to assess whether treatment effect is heterogeneous across pre-specified subgroups. For each subgroup analysis, the Cox proportional hazards model will be fit for time to first event including the subgroup as a stratification factor, and the treatment group and interaction between treatment and subgroup as covariates. The treatment effect within each subgroup level will be presented as a hazard ratio (dronedaron on top of usual care vs. usual care) and a 95% CI. Heterogeneity will be assessed by presenting the interaction P-value, using a two-sided test.

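### Entry to the on-treatment set depends on a first dose that only the dronedarone arm has to reach after randomization, and the on-treatment period has no defined start

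*Protocol*

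**What the plan says.** Protocol Section 9.2 (Analysis Sets) gives two sets. The intention-to-treat set takes everyone randomized "regardless of treatment initiation, discontinuation or switching". The on-treatment set is conditional: "All randomized participants who took the assigned treatment will be included in the analyses according to the intervention arm they were assigned". Its end is spelled out: a 5-day tail after stopping or switching, and more than 14 consecutive days off dronedarone counts as stopping. On attribution it says that "all events occurring until 5 days after discontinuation or switching to the other treatment group will be attributed to the randomized group". No start of the period is given.

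Section 6.2 has the central pharmacy send dronedarone by "shipment direct to the subject's mailing address of choice" and adds: "Subjects in the intervention arm will be contacted within 10 days of randomization to verify that they have received their study drug shipment", and also that they have begun taking it. Note 7 to the Schedule of Activities (Section 1.2) uses the same 10 days. The comparator has no dispensing step. Section 6 states: "Usual care will be defined as best-practice, guideline-directed therapy of AF".

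The set is used in two places. Section 9.3.6 puts all safety analysis in it. Section 9.3.7 says that, as sensitivity analyses, "the primary and key secondary objectives will be tested using the OT population during the on-treatment period". The primary endpoint in Section 9.3.2 is "Time from randomization to the first occurrence of unplanned cardiovascular hospitalization or death from any cause within 12 months of randomization", so its clock starts at randomization.

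**The concern.** Having taken the assigned treatment is something that happens after randomization, and in practice only one arm can fail it. A dronedarone participant who dies while the drug is in the post never qualifies for the on-treatment set. A usual-care participant who dies on the same day does. The same holds for a non-fatal event that prevents a first dose. Section 8.2 itself describes starting dronedarone as contraindicated after certain recent heart-failure decompensations, so a heart-failure admission in the gap is a plausible example. Such an admission is also a primary-endpoint component, a tier of the win ratio and a listed safety event.

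There is a second effect. If time runs from randomization, participants who do start bring their untreated days into the dronedarone arm as exposed time.

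At stake are the only safety comparison that the protocol defines and the named sensitivity analyses of the primary and key secondary objectives. In an open-label trial, neither should rest on an entry rule that works differently by arm.

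**Working it through.** **Inputs (Sections 9.4 and 9.5).** Usual-care cumulative incidence 10%, 20%, 25% and 30% at 3, 6, 9 and 12 months; 20% exponential loss by 12 months; 1500 per arm; hazard ratio (HR) 0.79; 733 events; two-sided alpha 0.05. The documents give neither the delay to first dose nor the share of pre-dose events that prevent a start, so both are varied.

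**1. Check of the event model.** The protocol states no figure for the on-treatment set, so its power figure is reproduced first.
- Power = Φ(√733/2 × |ln 0.79| − 1.96) = Φ(3.191 − 1.960) = 0.891; stated 0.89.
- Expected events with piecewise hazards from the curve and censoring at −ln(0.8)/12 per month: 411 (usual care) + 336 (dronedarone at 0.79) = 747. With a constant hazard: 738. Stated: 733.

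**2. Primary events before the first dose, per 1500.** The hazard in the first 3 months is −ln(0.90)/3 = 0.0351 per month, and a delay of d days is d/30.44 months.
- 5 days: 1500 × (1 − exp(−0.00577)) = 8.6
- 10 days: 1500 × (1 − exp(−0.01154)) = 17.2
- With a constant hazard over the year: 7.3 and 14.6

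At 10 days this is 17.2/411 = 4.2% of the arm's expected events under no effect.

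**3. True HR 1.00.** By event counts, losing all 17.2 gives (411 − 17.2)/411 = 0.958, and losing half gives 0.979. A Cox simulation with 1,000,000 per arm gives:

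| Pre-dose events lost, dronedarone arm only (10-day delay) | On-treatment HR |
|---|---|
| all | 0.96 |
| half | 0.98 |
| a quarter | 0.99 |
| 5% | 0.998 |

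With a 5-day delay and all lost it is 0.98.

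**4. True HR 0.79 after dosing, none before.** With p = 0.042 of events falling before the dose and a share k of them kept, the on-treatment HR is roughly 0.79 × (1 − p) + p × k.
- All kept (k = 1): 0.757 + 0.042 = 0.799 (simulation 0.802)
- Half kept: 0.757 + 0.021 = 0.778 (simulation 0.782)
- None kept: 0.757 (simulation 0.761)

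Setting the expression equal to 0.79 gives k = 0.79. The two effects cancel when about 21% of pre-dose events are lost. Below that the estimate is diluted against dronedarone; above it, the estimate favours dronedarone.

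**5. Common start.** Counting both arms from day 10 among those still event-free gives 1.001 and 0.793 for true values of 1.00 and 0.79. Simulation error is a few thousandths, so the asymmetry is gone.

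**6. Safety person-time.** If time runs from randomization, a 10-day delay puts 10/365 = 2.7% of a full-year participant's time into the dronedarone denominator unexposed.

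**The case against.** The strongest reply is that the primary and key secondary analyses use all randomized participants, that the on-treatment efficacy analysis is only a sensitivity analysis, and that Sections 9 and 9.3.1 leave technical detail to a statistical analysis plan that is not at hand. The start date of the period may be fixed there. That part stands: a missing start date alone would not be a finding. But the entry condition is not left open. Section 9.2 states it, and applied as written it works on one arm.

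A reader might infer several stronger things that the documents do not support.
- That every pre-dose event disappears from the dronedarone arm. A participant admitted before the first dose who starts later is in the set, and the attribution rule, which names no start, counts the event. It would be lost only if the period were read as beginning at first dose.
- That the drug takes 10 days to arrive. Ten days is the window for the verification contact, not a delivery time or a maximum.
- That usual care begins at the moment of randomization. This is inferred from the absence of a dispensing step.
- That the bias in the primary composite always favours dronedarone. Step 4 shows that it need not at HR 0.79.
- That early risk is raised because most participants are randomized around an acute encounter. Section 8 allows inpatient or outpatient enrolment up to 120 days after diagnosis and gives no proportions.

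Many of the causes in Table 1 are admissions after which a mailed drug could still be started, so the share lost may well be far below all.

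**Conclusion.** The defect is real and modest. Entry to the on-treatment set is conditional on a post-randomization step that in practice only the dronedarone arm must reach, and no common start restores the balance. The intention-to-treat primary analysis and the sample size are unaffected.

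For the primary composite with a true HR of 1.00 and a 10-day delay, the on-treatment HR is at worst 0.96, about 0.98 if half of the pre-dose events are lost, and close to 1.00 if few are. At HR 0.79 the result lies between about 0.80 and 0.76, with the sign of the error turning at roughly 21% lost. For mortality the share lost is complete by definition, since no one who dies before dosing can qualify, but the documents give no death rate from which to size it.

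These figures assume the protocol's event curve, a constant hazard within the first 3 months, the same delay for everyone, and no drug effect before the first dose. The point deserves correction mainly because every safety analysis depends on this set and the correction is cheap.

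**What to change.** Amend Section 9.2 as follows.

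1. **On-treatment efficacy.** Use the same start in both arms: a common landmark, for example day 10, among participants alive and event-free who have started assigned treatment. Count time from the landmark and let the existing 5-day rule handle later discontinuation. State how participants who never start, or start after the landmark, are handled, and report their number by arm. Some selection on starting remains, as in any on-treatment analysis.
2. **Safety.** Analyse all randomized participants from randomization alongside the on-treatment rates, so that early events in both arms are retained. Do not start dronedarone time at first dose while usual-care time starts at a landmark; that creates a new mismatch.
3. **First-dose date.** Take it from the contact already planned within 10 days. The case report form is not shown, so the date may already be collected.

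The cost is a few sentences, one additional set of safety tables and at most one date field. The landmark removes about 4% of primary events from each arm of the on-treatment analysis under no effect (17.2/411), and about 5% from the dronedarone arm at HR 0.79 (17.2/336). The primary analysis loses nothing.

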9.3. Statistical Analyses

9.3.1. General Considerations

- A detailed Statistical Analysis Plan (SAP) will be developed and contained in a separate document. Study population details including the number randomized to each treatment arm, the number completing the study, and lost to follow-up will be described. Baseline participant characteristics will be summarized as means, standard deviations, medians, and/or 25th, 75th percentiles for continuous variables, and as counts and percentages for categorical variables. Unless otherwise stated, tests of hypotheses about the efficacy of dronedarone will be one-sided ($\alpha=0.025$) and effect estimates will be presented with nominal 95% confidence intervals (CI).

9.3.2. Primary Efficacy Estimand Analysis

Question of Interest	Does the treatment with dronedarone on top of usual care reduce cardiovascular hospitalization or death from any cause in patients with first-detected atrial fibrillation without heart failure compared to usual care alone?
Objective Description / Study Population	Primary objective of the study / All randomized participants
Endpoint	Time from randomization to the first occurrence of unplanned cardiovascular hospitalization or death from any cause within 12 months of randomization

Intercurrent Events	Early study withdrawal or lost-to-follow-up: follow-up will be censored at the last date when patient event status was known. Analysis will assume that censoring is non-informative. All other intercurrent events will be ignored in these analyses.
Population Summary	Hazard ratio estimate based on a Cox proportional hazards model. Values below 1.0 suggest benefit from the treatment with dronedarone and usual care versus usual care alone.

The Cox proportional hazards model will be fit for time to first event with the treatment group as exposure variable. The treatment effect will be presented as a hazard ratio (dronedarone on top of usual care vs. usual care) and a 95% CI and P-value.

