6.1. Measures to Minimize Bias: Randomization

This is an open-label study; however, the specific intervention to be taken by an enrolled participant will be randomly assigned. Participants will be randomly assigned 1:1 to dronedarone on top of usual care or usual care alone. Randomization will be stratified by site and will be created with a random block size. All participants will be centrally assigned to randomized study intervention using an interactive web response system (IWRS). The site will contact the IWRS prior to the start of study intervention administration for each participant. The site will record the intervention assignment on the applicable case report form, if required. Potential bias will be reduced by the use of central randomization. Site staff and participants will not know the randomized sequence of treatment assignment prior to enrollment. Before the study is initiated, the log-in information and directions for the IWRS will be provided to each site.

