In addition to these routine safety reviews, an interim analysis for efficacy and futility of the primary objective is planned at approximately 50% of total information, i.e. when 50% of the expected total number of events (approximately 733 events, see **Table 4** below) are collected. The Lan-DeMets spending function similar to the O'Brien-Fleming boundaries will be used to monitor the efficacy of the primary outcome as a guide for the DSMB. See **Table 4** for the details of these procedures. This spending function is conservative in that priority is given to preserving power for the final analysis with the use of stringent stopping rules early in the study. For futility, conditional power will be calculated under originally hypothesized hazard ratio, the null hypothesis and the observed trend at the interim analysis and will be compared with 10%. The futility stopping rules will be considered non-binding by the DSMB in their review of interim data.

If the primary endpoint is declared to be statistically significant in the favorable direction at a one-sided alpha level of 0.025, WIN ratio as the first key secondary endpoint will be tested according to an OBF-like boundary. See **Table 4** for the details of these procedures.

Table 4. Significance level for the primary endpoint and WIN ratio

	At the interim analysis at 50%	At the final analysis	One-sided nominal significance level
One-sided significance level for the primary hypothesis	0.0153	0.0245	0.025
One-sided significance level for WIN ratio if the primary endpoint is declared significant	0.0153	0.0245	0.025

The Steering Committee will approve the timing of all interim analyses proposed by the DSMB. If the DSMB determines there is absence of futility, acceptable safety, and pre-trial assumptions regarding the endpoint event rate and other factors are correct, the trial will continue as planned.

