9.5. Sample Size Determination

- With a planned accrual time of 1.5 years, a fixed follow-up period of 1 year, an assumed lost to follow up of 20% before 12 months (assuming exponential distribution for time-to-censoring), a two-sample log-rank test with two-sided alpha of 0.05, a cumulative incidence function (CIF) of 30% at 12 months in the usual care arm, an assumed hazard ratio of 0.79, one interim analysis using the Lan-DeMets spending function similar to the O'Brien-Fleming boundaries, a planned sample size of 3000 patients (1500 patient per arm) provides approximately 89% study power as shown in the following table:

**Table 5. Study power and number of events with 3000 patients
Estimated by Markov chain Monte Carlo simulations with 10,000 iterations**

Hazard Ratio (Dronedarone vs. Usual care)	0.78	0.79	0.80
Nominal Power	0.92	0.89	0.86
Total number of events	730	733	737

[figure not shown]
- The study will be conducted at sites participating in the GWTG-AFIB Registry. Some sites will be centers that are established GWTG-AFIB sites and others will be recruited to participate in GWTG-AFIB for the purpose of this study. We will attempt to achieve a total of up to 200 sites. There have been more than 40,000 patients included in the GWTG-AFIB Registry. For the purpose of this pragmatic trial, patients will be approached at the time of their first-detected AF episode. Preliminary query of the GWTG-AFIB database suggests that greater than 1400 patients were enrolled each year in GWTG with new-onset AF and no heart failure. Using the Jan 2020 GWTG-AFIB data harvest, there were a total of 8,192 patients meeting the inclusion/exclusion criteria (see Table 6). As we plan to include sites beyond GWTG-AFIB sites, we plan to enrol 3000 patients in 18 months.

Table 6. Distribution of Admissions for GWTG-AFIB Registry Patients

Admission Year	Frequency (patients)	Percent	Cumulative Frequency (patients)	Cumulative Percent
2013	65	0.79%	65	0.79%
2014	390	4.76%	455	5.55%
2015	1229	15.00%	1684	20.56%
2016	1429	17.44%	3113	38.00%
2017	1750	21.36%	4863	59.36%
2018	1871	22.84%	6734	82.20%
2019	1458	17.80%	8192	100.00%

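### The primary Cox model names treatment only; prespecified adjustment for baseline variables already collected would add roughly 1 to 5 points of power at almost no cost

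*Protocol*

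**What the plan says.** Section 9.3.2 gives the primary model in one sentence: "The Cox proportional hazards model will be fit for time to first event with the treatment group as exposure variable". Sections 9.3.3.2 and 9.3.3.3 use the same form for cardiovascular hospitalization and all-cause mortality.

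On the design side, section 6.1 states: "Randomization will be stratified by site and will be created with a random block size". Section 9.5 says of the number of sites: "We will attempt to achieve a total of up to 200 sites".

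The schedule of activities (section 1.2) lists demographics, medical history and ejection fraction at baseline. Section 9.3.7 then names 15 baseline variables, including age, sex, AF type, heart failure and CHA₂DS₂-VASc, for subgroup work: "These analyses will focus on whether the relative therapeutic effect differs according to the following baseline variables".

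Sample size in section 9.5 rests on "a two-sample log-rank test with two-sided alpha of 0.05" and "an assumed hazard ratio of 0.79", with no covariates.

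**The concern.** A Cox model without prognostic covariates generally gives a weaker test of the treatment effect than one that includes them. The trial records likely predictors anyway, so adjusting for them needs no extra patients or visits.

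The protocol does name covariates or strata where it wants them. The quality-of-life ANCOVA in section 9.3.5 includes the baseline score, and the subgroup Cox models in section 9.3.7 are stratified by the subgroup. Where it defers a method to the SAP it says so, as for the tertiary endpoints in section 9.3.4. The treatment-only primary model therefore reads as a choice already made.

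What is at stake is margin. Table 5 shows power falling from 0.89 to 0.86 if the hazard ratio is 0.80 instead of 0.79, and both the event rate and the effect size are borrowed from ATHENA.

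**Working it through.** **1. Reproduce the stated power.** With D events and 1:1 allocation, power = Φ(√(D/4)·|ln HR| − z). Inputs are from section 9.5, Table 5.

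- HR 0.79, D = 733: √183.25 × 0.2357 = 3.191. At two-sided 0.05, Φ(3.191 − 1.960) = 0.891 (stated 0.89). At the final one-sided level of 0.0245 in Table 4, Φ(3.191 − 1.969) = 0.889.
- HR 0.78, D = 730: 0.919 (stated 0.92).
- HR 0.80, D = 737: 0.858 (stated 0.86).

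The stated power reproduces and does not depend on adjustment.

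**2. Simulate the effect of adjustment.** From the protocol: 3000 patients, usual-care cumulative incidence of 10/20/25/30% at 3/6/9/12 months, 20% exponential loss by 12 months, marginal HR about 0.79, up to 200 sites and one-sided 0.0245. Assumed, because the protocol gives no figure: a single normally distributed prognostic score with log-hazard SD 0.3 to 0.8, a between-site log-hazard SD of 0 or 0.3, unequal site sizes and blocks of 2, 4 or 6. There were 1600 trials per scenario and no interim look. Power = Φ(mean |z| − 1.969).

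The simulated trials average 747 to 748 events, against 733 in Table 5, so treatment-only power is 0.90 here and not 0.89. With between-site SD 0.3:

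| Covariate SD (C-index) | Mean abs. z, treatment only | Mean abs. z, adjusted | Ratio squared | Power | Gain (points) |
|---|---|---|---|---|---|
| 0.30 (0.59) | 3.266 | 3.313 | 1.029 | 0.903 → 0.911 | 0.8 |
| 0.45 (0.63) | 3.265 | 3.370 | 1.065 | 0.903 → 0.919 | 1.6 |
| 0.60 (0.665) | 3.267 | 3.456 | 1.119 | 0.903 → 0.932 | 2.9 |
| 0.80 (0.705) | 3.274 | 3.617 | 1.221 | 0.904 → 0.950 | 4.6 |

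The squared ratio is the equivalent gain in events. Multiplying the planned 3.191 by each z ratio puts the result on the protocol's own scale: power of about 0.90, 0.91, 0.92 and 0.94, against 0.89.

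**3. Check site separately.** 3000/200 = 15 patients and 733/200 = 3.7 events per site.

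- Site-stratified, no covariates, no site variation: mean |z| 3.264 → 3.216, power 0.902 → 0.894 (−0.8 points).
- Site-stratified, no covariates, between-site SD 0.3: a change of −0.1 to −0.2 points.
- Covariates plus full site strata: gains of about 0.5, 1.2, 1.7 to 2.3, and 3.8 points in the four scenarios, below covariates alone each time.
- The treatment-only z had an SD of 0.99 to 1.01 with between-site SD 0.3, so leaving site out did not distort the standard error.

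**4. Check the target of estimation.** With a marginal HR of about 0.79, the conditional HR was 0.784, 0.781, 0.775 and 0.766 in the four scenarios.

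**5. Price a point of power.** In Table 7 at HR 0.79, going from 0.89 to 0.90 takes 3056 − 2954 = 102 patients. The weakest scenario is then worth about 0.8 × 102 ≈ 82 patients.

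**The case against.** The strongest reply is that nothing is wrong. A treatment-only Cox model is valid, it matches the unadjusted log-rank test behind the sample size, and the promised 89% is delivered without covariates. All of that stands.

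A second reply is that covariates are typical SAP content, and that section 9 and section 9.3.1 promise a more detailed SAP, which is not shown here. This stands in part. The SAP may add covariates, but section 9 describes it as elaborating the analyses stated there, and the stated model has one term.

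Third, prognostic strength is unknown and could be low. The endpoint mixes many kinds of cardiovascular admission, and the exclusions remove NYHA III/IV, recent heart failure admission and LVEF of 40% or below. Data come from usual care with no required tests (section 1.2 footnote 1, section 8), so some covariates will be incomplete. This is why the gain is given as a range starting below one point, and why the covariates must be well-captured ones. The simulated score was complete and correctly modelled, which favours adjustment.

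Fourth, section 9.4 already provides a blinded power review aiming at 85% or more, with up to 35% more patients. The 0.86 at HR 0.80 is above that target. But that route costs enrolment, while adjustment does not.

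Finally, the planned 0.79 comes from event rates by arm and is a marginal quantity. The adjusted model estimates something slightly different, so its smaller hazard ratio is partly a change of target and not the removal of a bias. This stands and has to be stated in the estimand.

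**Conclusion.** The point holds as an efficiency recommendation. Prespecified covariate adjustment would raise primary power by about 1 to 5 points, if the chosen covariates carry a log-hazard SD of 0.3 to 0.8. The protocol neither supports nor excludes that range. A gain of 2 to 4 points would need a C-index of about 0.64 to 0.69.

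Three stronger readings are tempting and are not supported:

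- **That omitting site wastes power.** A reader might infer this from randomization stratified by site. In the calculations, full site stratification never gained power and cost 0.1 to 0.8 points.
- **That the primary analysis is wrong or its power overstated.** The test is valid and the stated 0.89 reproduces.
- **That power is also lost for cardiovascular hospitalization and mortality.** Section 9.1.1 limits formal testing to the primary endpoint and the WIN ratio, so those two hazard ratios are reported with nominal intervals only.

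**What to change.** Before any comparison by arm is seen, change section 9.3.2 and carry the change into the SAP:

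- Define the primary Cox model as treatment plus a short fixed list of well-captured baseline covariates, for example age, sex, heart failure, AF type and CHA₂DS₂-VASc. Use the same model at the interim and final looks.
- State a simple rule for missing covariate values, so that no randomized participant drops out of the analysis.
- State in the population-summary row of the estimand table that the hazard ratio is conditional on the listed covariates.
- Report the unadjusted hazard ratio as supportive.
- State how site is handled: shared frailty, strata with small sites pooled, or a sensitivity analysis. Claim no power gain from it.
- If the same model is used for cardiovascular hospitalization and mortality, present that as consistency only.

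The cost is wording, the missing-data rule and a slightly different target of estimation. No data collection is added and the sample size can stay as planned. If the sponsor keeps the treatment-only model, one sentence giving the reason would be enough.
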